	22.3 Audits	
23.	QUALITY CONTROL AND QUALITY ASSURANCE	. 33
24.	ETHICAL CONSIDERATIONS	. 33
25.	STUDY TERMINATION	. 34
26.	PUBLICATION POLICY	. 34
27 .	REFERENCES	. 34
APF	PENDIX A- INSTRUCTIONS FOR USE OF 3M™ CAVILON™ ADVANCED SKIN PROTECTANT	35
APF	PENDIX B	. 39
APF	PENDIX C – CRFS	. 40
APF	PENDIX D – PHOTOGRAPHIC INSTRUCTIONS	. 41
APF	PENDIX E – INFORMED CONSENT	. 42

Page 7 of 43 Status: Release Version: 1

Issue Date: 10/5/2016 9:39:53 AM

1. Protocol Synopsis

Study Title	A Pilot Study Evaluating the Use of 3M™ Cavilon™ Advanced Skin Protectant in the Management of Damaged Skin Around an Ostomy, Drain and/or Fistula				
Study Product & Regulatory Status:	3M™ Cavilon™ Advanced Skin Protectant is a 510(k) cleared medical device.				
Randomization	This is a pilot study with no randomization. Sample size: 30 (approximately 10 subjects with an ostomy, drain, or fistula.)				
Study Objective(s) & Hypothesis:	Objective(s): The primary objective of this pilot study is to evaluate the feasibility, safety and efficacy of 3M [™] Cavilon [™] Advanced Skin Protectant when used in the management of damaged skin exposed to caustic body fluids from an ostomy, drain site or fistula.				
Outcome Measures:	Primary Efficacy Endpoint:				
	There are two primary endpoints. The first primary endpoint is the improvement of denuded skin (defined as clinical improvement from the baseline skin assessment) of the primary site of interest (ostomy, drain, or fistula). The second primary endpoint is a comparative pain score using the Faces Pain Visual Analog Scale comparing baseline to the end of study.				

Page 8 of 43 Status: Release Version: 1

Issue Date: 10/5/2016 9:39:53 AM

Study Population:	Inclusion/Exclusion Criteria:
	Subjects may be enrolled into this study if the answers to all these questions are yes .
	1. Is the subject 18 years of age or older?
	2. Does the subject have red skin with breakdown (i.e. skin erosion and denudation or denudation of skin alone) at the primary site of an ostomy, drain and/or fistula?
	3. Is the subject willing to have photographs taken of their skin and permit use of photographs in potential publication?
	4. Is the subject willing to release rights to 3M for the use of the photos?
	5. Is there a reasonable expectation that the subject will be in the hospital or available for follow-up visits during the 14 day study period?
	6. Has the subject signed an Institutional Review Board-approved informed consent/assent document and authorized the use and disclosure of protected health information?
	Subjects are excluded from participation in this study if any of the answers to these following questions is yes.
	1. If female, is the subject pregnant or breast feeding or has she given birth within the 3 weeks preceding the screening visit?
	2. Does the subject have a known allergy to acrylates or cyanoacrylates?
	3. Does the subject have a preexisting skin disease on the areas affected that may make skin assessments for this study difficult?
	4. Does the skin area affected require treatment with a concomitant medication or product?
	5. Has the subject received antifungal powders in the area affected within 24 hours prior to enrollment?
	6. Has the subject received cyanoacrylate based skin protectant (such as Marathon) within 72 hours prior to enrollment?
	7. Does the subject have any medical condition that in the opinion of the investigator should exclude him/her from participating in the study?
	8. Has the subject been enrolled in any investigational study where product was applied to proposed study sites within 30 days of the screening visit?
Study Design:	Prospective pilot intervention study
Sample Size:	Maximum of 30 subjects
Geography:	Single site in USA over a period of up to 15 months
# Sites:	Estimated # of sites: 1
	# of Subjects per site: up to 30 subjects

Page 9 of 43 Status: Release Version: 1

Issue Date: 10/5/2016 9:39:53 AM

Assessments:	Study Assessments:
	Subjects will be screened for the Inclusion/Exclusion criteria
	History, demographics, and medications will be documented at baseline.
	 Subjects will remain in the study for up to 14 days following enrollment, receiving the product. Skin assessments will be performed on product dosing days. Assessments will be done using a clinical skin assessment (described below) and photographs.
	 Subject's response regarding pain scores will be tracked following cleansing and product application.
	Quantity of products used will be tracked.
	Data Sets Analyzed:
	The primary efficacy data set will be the data set that will consist of subjects who have at least one skin assessment post-baseline. Dropouts will be censored at time of dropping out.
	Efficacy Analysis:
	 The primary response will be the percent change in area of epidermal loss between the areas observed at baseline subtracted from the area of epidermal loss at each time point. In addition, the time to re-epithelialization will be estimated using a Kaplan-Meier method. These will be summarized overall as well by each type of site (ostomy, drain, and/or fistula).
Data Analysis Planned:	 Pain scores assessed by the visual analog scale will be compared between baseline and each time point post-application of the barrier film. A paired t-test will be done to assess the significance of the change from baseline. These will be summarized overall as well by each type of damaged skin (ostomy, drain, and fistula).
	•
	 Safety Analysis: Overall incidence of adverse events will be documented. The safety analysis data set will consist of all subjects enrolled in the study who received at least one application of the test material.

Page 10 of 43 Status: Release Version: 1

Issue Date: 10/5/2016 9:39:53 AM

2. Background Information

The skin is the protective layer of the body and provides an important anatomical barrier to pathogens, irritants, water loss and environmental threats. Various conditions can damage the skin and breach integrity of the barrier. This can result in inflammation, disruption of epidermal integrity, pain and can increase the risk of infection.

Intact, dry skin, and containment of effluent with a well-fitted pouching system is imperative in the management of ostomies, high output fistulas, and leaking drain sites. When skin integrity is compromised, the cyclical pattern of pouch leakage/skin erosion/pouch leakage must be broken to enable epidermal resurfacing and restoration of an intact seal. Treatment of the skin relies on methods to create dry surfaces. Intact epidermis is maintained with skin barrier. Standard of care technique to ensure denuded skin is dry before applying a pouching system is called "crusting". In this technique, the affected area is cleaned and dried. Dust stoma powder is applied over the affected tissue, with excess brushed away. The skin barrier is applied and allowed to dry, and may be repeated multiple times to provide a protective seal that allows the skin to re-epithelialize. If the area becomes contaminated with moisture, stool, urine, or wound drainage, the powder may become wet, necessitating that the process start over. This technique is time consuming and can be complex for some patients.

Standard of care techniques and products do not always appropriately resolve the situation at hand, or may take additional applications. However, newer approaches involve the formation of an adequate dry surface by the application of cyanoacrylate. It is applied to the irritated tissue, allowed to dry resulting in an immediate barrier film to form. Then the wafer or pouch is applied. There is currently one skin protectant formula on the market to address partial thickness, moisture-associated skin damage secondary to ostomy, fistula, or drains. While this product is effective, patients frequently note pain or discomfort upon application.

3M[™] Cavilon[™] Advanced Skin Protectant is a new skin protectant formulated to protect damaged and denuded skin, even in the presence of exposure to the most potentially damaging body fluids, such as liquid stool and gastric fluid. The benefit of utilizing this product is that it does not cause discomfort on application and appears to be as effective as the product currently on the market.

Page 11 of 43 Status: Release Version: 1

Issue Date: 10/5/2016 9:39:53 AM

This pilot study will examine the safety and efficacy of this novel technology to create an optimal environment where healing can occur by virtue of its ability to adhere to severely damaged or intact moist or wet skin, thus providing protection from liquid feces and other irritating body fluids. This study will also examine if this product is comfortable for subjects during application and wear. In addition, this product is easily cleaned and does not require frequent removal, making it more clinician friendly than paste barriers. If this product is equivalent to the current product while causing less discomfort upon application and throughout the use of the product, this may be an alternative option to offer patients.

3. Device Description and Regulatory Status

3M™ Cavilon™ Advanced Skin Protectant is a 510(k) cleared medical device. The product, and its use in the study, poses a non-significant risk to the participants, and intends to conduct the study under the abbreviated IDE requirements at 21 CFR §812.2(c). The device does not meet the requirements of a significant risk device since it is not an implant, not being used to support or sustain life, not being used for diagnosing, curing, mitigating, or treating disease, and does not present a potential for serious risk to health, safety, and welfare of a subject. The product is an acrylate polymer technology that utilizes cyanoacrylate(s) as a component of the formulation. This formulation is delivered from a non-stinging, rapid drying solvent. Upon application to the skin it forms a breathable, transparent coating.

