6.3 Sample Size

A maximum of 30 subjects (10 subjects each for ostomy, drain and fistula) will be enrolled. A sample size of 30 is usually sufficient to estimate the distribution of a population and provide an estimate of performance for future studies.

Page 15 of 43 Status: Release Version: 1

Issue Date: 10/5/2016 9:39:53 AM

6.4 **Study Duration**

In order to screen, enroll, and complete up to 30 evaluable subjects, an enrollment period of is anticipated. 3M™ Cavilon™ Advanced Skin Protectant is indicated for application every 72 hours. Patient will return or be seen inpatient every 72 hours (±24 hours) for evaluation of product application. Assessment of denuded surface area will be measured at baseline. follow-up visits, and at the end of the study typically at day 14 but may be sooner if wound resolves at an earlier date. As previously noted, each subject may be followed for up to 14 days.

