10.3 Schedule of Events

Assessment	Screening / Enrollment Day 0	Week 1 Day 3 (± 24 hours)	Week 1 Day 6 (± 24 hours)	Week 2 Day 9 (± 24 hours)	Week 2 Day 12 (± 24 hours)	Unscheduled Visit (any time there is an issue with the site)	End of Study or Day 14
Informed Consent	Х					,	
Inclusion/Exclusion	Х						
Urine Pregnancy Test	х						
Demographics	Х						
History & Current Product Use	х						
Medications	Х	Х	Х	Х	Х	Х	Х
	Х						Х
Skin Cleansing	Х	Х	Х	Х	Х	Х	Х
Skin Assessment / scoring	х	X	Х	Х	Х	Х	Х
Photographs	Х	Х	Х	Х	Х	Х	Х
Product Application	Х	Х	Х	Х	Х	Х	
Adverse Events	Х	Х	Х	Х	Х	Х	Х
							Х
Protocol Deviation	Х	Х	Х	Х	Х	Х	Х

Page 22 of 43 Status: Release

Version: 1

Issue Date: 10/5/2016 9:39:53 AM

11. Subject Discontinuation

The Investigator may discontinue individual subjects from the study at any time. Subjects may voluntarily withdraw from the study at any time. The Investigator or study nurse will indicate on the appropriate CRF reason for, and date of, subject discontinuation.

Possible reasons for discontinuation are listed below:

- A subject develops a bacterial or fungal infection in the area included in the study or any
 other condition requiring the use of a topical treatment. Data collected up to the time where
 the subject required topical treatment will be analyzed.
- A subject develops any condition which, in the opinion of the Investigator, requires
 discontinuation from the study. If this condition is a suspected localized allergic reaction to
 the product, then appropriate testing confirmation should be performed and results/reports
 should be submitted to 3M. In addition, the event should be entered on the Adverse Event
 CRF.

The expectation is that subjects will be enrolled in this study for a period up to14 days. A subject who discontinues prior to their first assessment following product application, will be replaced with another qualified subject.

12. Subject Compliance

Subject compliance is not an issue in this study as subjects will not be applying the product themselves. CRFs will be used to monitor the number of cleansing episodes, and number of product application(s), performed by skilled care givers.

13. Study Supplies

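### Healing curve: censoring site- and product-related stops can put the Kaplan-Meier figure above the share healed on the product by Day 14

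*Combined protocol and SAP*

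**What the plan says.** The synopsis (Section 1, Data Sets Analyzed) defines the set: "The primary efficacy data set will be the data set that will consist of subjects who have at least one skin assessment post-baseline". It then gives one rule for leaving, without regard to reason: "Dropouts will be censored at time of dropping out". The synopsis and Section 17.1.1 both plan a Kaplan-Meier estimate of time to re-epithelialization, in addition to the percent change in epidermal loss, overall and by site type.

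Section 11 gives possible reasons for stopping. One is "A subject develops a bacterial or fungal infection in the area included in the study or any" other condition needing a topical treatment. For these subjects, data up to the time when "the subject required topical treatment will be analyzed". The other is "A subject develops any condition which, in the opinion of the Investigator, requires" stopping, with a suspected localized allergic reaction to the product as the example. Section 11 also says: "A subject who discontinues prior to their first assessment following product application, will be replaced with another qualified subject". Those very early leavers are outside this point. On recording it says: "The Investigator or study nurse will indicate on the appropriate CRF reason for, and date of, subject discontinuation".

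Section 17.4 censors, in the healing-time estimate, data missing because a subject finishes early, and leaves other missing data to the Statistical Analysis Plan. Section 6.4 places the end of study typically at Day 14, or earlier if the wound resolves. No section says which Day 14 quantity the curve estimates.

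**The concern.** Kaplan-Meier censoring treats a subject who leaves as someone who would have gone on to heal at the same rate as those who remain. For a subject stopped because the site became infected, needed topical treatment or appeared to react to the product, no section states or supports that assumption.

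Whether it matters depends on the question. The curve could describe healing had nobody needed to stop, or healing actually achieved on the product by Day 14. Section 6.3 says that the sample should "provide an estimate of performance for future studies". A Day 14 figure used that way could well be read as the share healed on the product. On that reading a subject stopped for a site or product reason did not heal on the product, and removing that subject from the risk set gives more weight to later healings. The effect is largest in the site-type groups of about 10, where one exit moves the curve most.

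**Working it through.** **Inputs from the documents.** At most 30 subjects, 10 per site type (Section 6.3); visits at Days 3, 6, 9, 12 and 14 (Section 10.1); censoring without regard to reason (synopsis). The plan states no healing rate, exit rate or healing percentage, so there is no figure of its own to reproduce. All counts below are assumed. Exits are unhealed subjects with at least one post-baseline assessment. At a shared visit, healings are counted before exits.

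**Direction.** At each visit let n be at risk, d heal and x stop for a site or product reason.
- 1-KM = sum of KM(t-) x d/n, where KM is the product of (1 - d/n).
- Cumulative incidence = sum of S(t-) x d/n, where S is the product of (1 - (d + x)/n).

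No factor of S exceeds the matching factor of KM, so 1-KM cannot be below the cumulative incidence. They are equal when no such exit precedes a later healing. For 6 subjects, each with one of 15 outcomes (5 visits; healed, stopped or otherwise censored), there are 38,760 patterns: 1-KM was lower in none, equal in 20,020 and higher in 18,740.

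**Size at n = 30, healed count fixed.** With no other censoring, the cumulative incidence is healed/30. Healing patterns: 10 = 2/3/3/2 and 16 = 4/4/4/4 at Days 6/9/12/14; 20 = 2/5/5/4/4 at Days 3/6/9/12/14. Exits are early (all at Day 3), spread (equally over Days 3, 6 and 9) or late (3 exits: 1 at Day 9 and 2 at Day 12; 6 exits: 3 at each).

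| Healed | Share healed | 1-KM, 3 exits (early / spread / late) | 1-KM, 6 exits (early / spread / late) |
|---|---|---|---|
| 10 | 33.3% | 37.0 / 36.4 / 34.8% | 41.7 / 40.1 / 37.0% |
| 16 | 53.3% | 59.3 / 58.4 / 56.5% | 66.7 / 64.9 / 61.4% |
| 20 | 66.7% | 73.9 / 73.0 / 70.8% | 83.0 / 81.5 / 78.0% |

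Examples:
- 16 healed, 3 early exits: 1 - (23/27)(19/23)(15/19)(11/15) = 16/27 = 59.3%.
- 20 healed, 6 early exits: 1 - (28/30)(17/22)(12/17)(8/12)(4/8) = 1 - (28/30)(4/22) = 83.0%, against 20/30 = 66.7%, an excess of 16.4 points.

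Over every placement of the exits, the excess runs from 0 (all at Day 14) to 3.7, 5.9 and 7.2 points with 3 exits, and to 8.3, 13.3 and 16.4 points with 6 (10, 16 and 20 healed). The Greenwood standard error is 7.7 to 10.2 points, so 3 exits stay inside it and 6 can exceed it.

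**Size at n = 30, per-visit healing chance fixed.** Here exits reduce the number healed and 1-KM stays put. With 1-KM at 53.3% and 3 early exits, the share healed is (27/30)(16/30) = 48.0%; with 6 it is (24/30)(16/30) = 42.7%. Over the three patterns and timings, the excess is 1.3 to 6.4 points with 3 exits and 2.9 to 12.9 with 6.

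**One site type, n = 10, 5 healed** (1/1/2/1 at Days 6/9/12/14). One exit at Day 3, 6, 9, 12 or 14 gives 1-KM of 55.6, 55.0, 54.3, 52.0 or 50.0%, against 50.0%. The excess of 0 to 5.6 points lies inside a standard error of about 16 to 17.5 points.

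**What can move the curve otherwise.**
- Unrelated dropouts: suppose 2/3/3/2/1 heal at the five visits and 6 leave at Day 3. Then 1-KM = 1 - (28/30)(13/22) = 44.8%. If all 6 would have healed, the true share is 17/30 = 56.7%; if none would, it is 11/30 = 36.7%.
- Section 17.4 read literally: in the 16-healed pattern without exits, censoring the 12 who heal before Day 14 leaves 18 at risk and 4 events, so 1-KM = 4/18 = 22.2% against 53.3%.

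**The case against.** **The rule is less settled than it looks.** Dropout is not defined. Section 11 distinguishes stops by the Investigator from voluntary withdrawal, and a stop for infection may fall under the missing data that Section 17.4 leaves to the Statistical Analysis Plan. This stands in part: that these exits are censored is an inference. But the synopsis sentence is the only rule given for leaving, and no section treats the exits in any other way.

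**The plan promises no Day 14 healed percentage.** Censoring at discontinuation is a conventional choice, and infection does not make healing impossible, so treating it as a competing event is also a choice. This stands. If the target is healing had nobody stopped, the bias could go either way. It is a reason to state the target and show both figures, not to call Kaplan-Meier wrong.

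**A reader might infer that the planned curve can never be too low.** The documents do not support that. The one-way direction covers only site- and product-related exits, with healing coded as the event. Unrelated dropouts can bias either way, and the literal reading of Section 17.4 pulls the curve far down.

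**A reader might also infer that these exits disappear from the report.** They do not: Section 6.7 summarizes discontinuations by reason.

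**The sizes are assumed.** The 16.4-point case needs 6 of 30 to stop at Day 3 and 20 of the other 24 to heal; nothing in the documents points to such rates. This stands.

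**Conclusion.** The concern holds in a limited form. On the natural reading of the synopsis, site- and product-related stops are censored, and 1-KM is then equal to or above the cumulative incidence of healing on the product. The direction is algebraic, given that healing is the event and that the comparison concerns these exits alone. The size cannot be fixed from the documents. It is zero when no such exit precedes a later healing, and under the assumed counts it reaches about 7 points with 3 exits and about 16 with 6.

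A second defect stands apart: Sections 17.4 and 6.4 must be reconciled so that a subject who finishes early because the skin healed is not censored.

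The stakes are minor to moderate. This is a single-arm pilot without formal testing, and the healing curve is an additional, descriptive estimate.

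**What to change.** Add to the synopsis and to Section 17.4:

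> For time to re-epithelialization, the event is the first visit with 0% epidermal loss at the primary site, including when healing ends participation early. Beside the Kaplan-Meier estimate, the cumulative incidence of healing to Day 14 will be reported overall and by site type. Discontinuation for a reason related to the study site or the product, by the reason on the CRF and classed before analysis, is a competing event. The number of such exits will be shown.

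The planned Kaplan-Meier estimate stays, so both readings are available. No new data are needed: the percentage of epidermal loss is assessed at each visit (Section 10.1), and the reason and date of discontinuation are recorded (Section 11). Section 17.5 provides for documenting the change in the Statistical Analysis Plan before final analysis.

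The cost is a little more analysis and some judgement in classing exits, which matters in an unblinded study and is why the classing should be done before analysis. The added healing figure will be the same as the Kaplan-Meier figure or less favourable. The percent-change primary response and all clinical stopping rules are unchanged.

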3.1 Intended Use

Cavilon™ Advanced Skin Protectant forms a film barrier intended to protect intact or damaged skin. It is effective in conditions where skin is frequently or continuously exposed to moisture and caustic irritants such as feces, digestive fluids, wound drainage and urine. Cavilon™ Advanced Skin Protectant can also be used in areas exposed to friction and shear from bedding, clothing, shoes, or any other material that would rub against the skin.

4. Summary of Previous Studies

3M™ Cavilon™ Advanced Skin Protectant has been tested in a clinical pilot study, animal studies, and several healthy human volunteer studies including a durability study and a thermal pilot study. Summaries for these studies are included below.

4.1 Clinical Pilot Study

Page 12 of 43 Status: Release

Version: 1

Issue Date: 10/5/2016 9:39:53 AM

4.2 Animal Studies

4.3 Healthy Human Studies

[figure not shown]

Page 13 of 43 Status: Release

Version: 1

Issue Date: 10/5/2016 9:39:53 AM

4.4 Durability Study

Page 14 of 43 Status: Release Version: 1

16 0.20.52 AM

Issue Date: 10/5/2016 9:39:53 AM

3M[™] Cavilon[™] Advanced Skin Protectant is a new skin protectant formulated to protect damaged and denuded skin even in the presence of exposure to the most potentially damaging body fluids, such as liquid stool and gastric fluid.

This pilot study will determine if 3M™ Cavilon™ Advanced Skin Protectant is effective for subjects with skin damage in areas exposed to caustic body fluids including ostomies, drains and fistulas. 3M™ Cavilon™ Advanced Skin Protectant can be used on multiple sites on a subject. The primary site **must** have red skin with breakdown (i.e. skin erosion and denudation or denudation of skin alone). Secondary sites can have red skin with or without breakdown.

